10.1.2 Serious Adverse Event (SAE)

An AE that meets one or more of the following criteria/outcomes is classified as serious:

- Results in death;
- Is life-threatening (at immediate risk of death);
- Requires admittance to the hospital or prolongation of existing hospitalization;
- Results in persistent or significant disability/incapacity;
- Results in congenital anomaly/birth disfigurements among the offspring of the patients;
- Events with medical significance or needing medical intervention to prevent the occurrence of any of the above events.

Medical judgment should be exercised in deciding whether expedited reporting is appropriate in other situations, such as important medical events that may not be immediately life-threatening or result in death or hospitalization, but may jeopardize the patient or may require intervention to prevent one of the other outcomes listed in the definition above. Serious also includes any other event that the Investigator or Sponsor judges to be serious, or which is defined as serious.

AEs associated with in-patient hospitalization, or prolongation of an existing hospitalization, are considered serious. Any initial admission, even if the duration is less than 24 hours is considered serious. In addition, any transfer within the hospital to an acute/intensive care unit is considered serious. However, the following hospitalizations should not be considered serious:

- Hospitalization or prolonged hospitalization in the absence of precipitating clinical adverse events as follows:
 - Admission for treatment of preexisting condition not associated with the development of a new AE or with a worsening of the preexisting condition
 - Administrative admission (e.g., for a yearly physical examination)
 - Protocol-specified admission during the study (e.g., admission for SL-401 treatment)
 - Preplanned treatments or surgical procedures
 - Admission exclusively for the administration of blood products

Progress of the disease under study (including signs and symptoms of progression) should not be reported as an SAE unless the outcome is fatal during the study or within the safety reporting period. If the disease under study has a fatal outcome during the study or within the safety reporting period, then the event leading to death must be recorded as an AE and as a SAE with CTCAE Grade 5. Disease progression is NOT an SAE; however, some sequelae of disease progression (i.e., pain, thrombocytopenia) may be reported as AEs or SAEs (generally not related to investigational therapy).

The onset date of an SAE is defined as the date on which the event initially met serious criteria (e.g., the date of admission to a hospital). The end date is the date on which the event no longer met serious criteria (e.g., the date the patient was discharged from a hospital).

10.2 Period of Observation

Clinical signs and symptoms and AEs (regardless of relationship to study drug) will be collected continuously from the first day of SL-401 treatment to 30 days following the last infusion of SL-401. All SAEs and AEs judged to be related to study drug will be collected throughout the follow-up period.

Conditions that the patient experienced prior to SL-401 treatment should be recorded in the patient medical history section of the eCRF. All the AEs should be followed-up at the discretion of the Investigator until the symptoms dissipate or become stable even if AEs continue beyond the period of observation. AEs unresolved at the end of the observation period will be considered “ongoing” with an undetermined outcome; however, if after the period of observation completes but prior to the completion of the study, additional outcome information becomes available, it will be reported. The severity of the signs, symptoms, or AEs should be determined using the National Cancer Institute (NCI) Common Terminology Criteria for Adverse Events (CTCAE), Version 4.03. A complete CTCAE list can be downloaded at <http://evs.nci.nih.gov/ftp1/CTCAE/About.html>.

All clinically meaningful abnormal test results should be retested. Abnormal test results that are difficult to associate with the study drug should be followed until normalized or until the abnormality could be clearly attributed to another cause. Abnormal test results should not be reported as AEs unless they meet the criteria outlined in Section 10.1.1.

10.3 Pre-existing Conditions

A pre-existing condition will not be reported as an AE unless the condition worsens by at least one CTCAE grade during the study. The pre-existing condition, however, must be recorded in the screening eCRF as a pre-existing condition and all related concomitant medication administered for the condition recorded in the baseline (prior) concomitant medication eCRF.

10.4 Pregnancy

WOCBP and men with partners of childbearing potential must be using an adequate method of contraception to avoid pregnancy throughout the study and for up to 8 weeks after the study in such a manner that the risk of pregnancy is minimized. WOCBP include any female who has experienced menarche and who has not undergone successful surgical sterilization (hysterectomy, bilateral tubal ligation, or bilateral oophorectomy) or is not postmenopausal (defined as amenorrhea ≥ 12 consecutive months; or women on hormone replacement therapy with documented serum follicle-stimulating hormone level ≥ 35 mIU/mL). Even women who are using oral, implanted, or injectable contraceptive hormones or mechanical products, such as an intrauterine device or barrier methods (diaphragm, condoms, spermicides) to prevent pregnancy,

are practicing abstinence, or whose partner is sterile (e.g., vasectomy), should be considered to be of childbearing potential.

WOCBP must have a negative serum or urine pregnancy test at screening. If the pregnancy test is positive, the patient must not receive study therapy and must not be enrolled in the study.

Sexually active WOCBP must use an effective method of birth control during the course of the study, in a manner such that the risk of failure is minimized.

Prior to study enrollment, WOCBP must be advised of the importance of avoiding pregnancy during study participation and the potential risk factors for an unintentional pregnancy. This information will be included in the ICF that must be signed by the patient.

In addition, all WOCBP or fertile men with partners of childbearing potential should be instructed to contact the Investigator immediately if they suspect they or their partner might be pregnant (e.g., missed or late menstrual period) at any time during study participation.

If following initiation of study drug, it is subsequently discovered that a patient is pregnant or may have been pregnant at the time of exposure to study therapy, including during at least 2 months after product administration, study therapy will be permanently discontinued in an appropriate manner. Exceptions to discontinuation may be considered for life-threatening conditions only after consultation with the Sponsor and Medical Monitor or as otherwise specified in this protocol. The Investigator must immediately notify the Sponsor and Medical Monitor of this event.

Protocol-required procedures for study discontinuation and follow-up must be performed on the patient unless contraindicated by pregnancy (e.g., x-ray studies). Other appropriate pregnancy follow-up procedures should be considered if indicated. In addition, the Investigator must report to the Sponsor follow-up information regarding the course of the pregnancy, including perinatal and neonatal outcome. Infants should be followed for a minimum of 8 weeks.

10.5 Documentation and Reporting of Adverse Events by Investigator

The Investigator is to report all directly observed AEs spontaneously reported by the patient using concise medical terminology. In addition, each patient will be questioned about AEs at each clinic visit following initiation of treatment. The question asked will be “Since your last clinic visit have you had any health problems?” or a similar question to assess health status.

The AE reporting period for this study begins upon initiation of SL-401 treatment and ends 30 days after the last infusion of SL-401. All AEs are to be reported on the AE eCRF.

All AEs that occur in study patients during the AE reporting period specified in the protocol must be reported to the Sponsor, whether or not the event is considered study drug-related. In addition, any untoward event that occurs beyond the AE reporting period that the Investigator assesses as related to the investigational product should also be reported as an AE.

Each AE is to be classified by the Investigator as serious or non-serious. This classification of the gravity of the event determines the reporting procedures to be followed. If a SAE occurs, reporting will follow local and international regulations, as appropriate.

For any event that meets one of the SAE criteria, the Investigator must notify the Safety Contact **within 24 hours** of the knowledge of the occurrence. To report the SAE, complete the SAE form and email to the Safety Contact (email address listed below) or fax the completed paper SAE form to the Safety Contact (fax number listed below) within 24 hours of awareness.

[REDACTED]

[REDACTED]

Each SAE should be followed until resolution, or until such time as the Investigator determines its cause or determines that, it has become stable.

Within 24 hours of receipt of follow-up information, the Investigator must update the SAE form electronically in the EDC system for the study and submit any supporting documentation (e.g., patient discharge summary or autopsy reports) to the Safety Contact via fax or e-mail.

The Sponsor will report AEs, which are unexpected and reported as serious and associated with use of the study drug, to the US FDA and all participating clinical sites. For events that are fatal or life-threatening, unexpected, and associated with use of the investigational product, a 7-Day Alert Report will be submitted to the FDA within 7 calendar days of receipt of the SAE information. For all other events that are serious, unexpected, and associated with the use of the investigational medicinal product, a written report will be made no more than 15 calendar days from the date the Sponsor learns of the event.

10.6 Assessment of Causal Relationship to SL-401

In this study, the investigational medicinal product is SL-401. The relationship of an AE to the investigational product should be classified using the following guidelines:

- Related: A temporal relationship exists between the event onset and administration of SL-401. It cannot be readily explained by the patient's clinical state, intercurrent illness, or concomitant therapies. In case of cessation or reduction of the dose, the event abates or resolves and reappears upon rechallenge. This includes events that are considered possibly, probably, or definitely related to SL-401.
- Not Related: Evidence exists that the AE has an etiology other than the study drug (e.g., pre-existing condition, underlying disease, intercurrent illness, or concomitant medication). This includes events that are considered probably not or not related to SL-401. It should be emphasized that ineffective study drug treatment should not be considered as causally related in the context of AE reporting (in other words, disease progression is not considered an AE; however some sequelae of disease progression may be reported as AEs and should generally be reported as AEs not related to investigational therapy).

An Investigator who is qualified in medicine must make the determination of relationship to the investigational product for each AE. The Investigator should decide whether, in his or her medical judgment, there is a reasonable possibility that the event may have been caused by the investigational product. The following factors for study drug relationship should be referenced when making a determination of “related” or “not related.”

- The temporal sequence from study drug administration: The event should occur after the study drug is given. The length of time from study drug exposure to event should be evaluated in the clinical context of the event.
- Underlying, concomitant, intercurrent diseases: Each report should be evaluated in the context of the natural history and course of the disease being treated and any other disease the patient may have.
- Concomitant medication: The other medications the patient is taking or the treatment the patient receives should be examined to determine whether any of them might be recognized to cause the event in question.
- Known response pattern for this class of study drug: Clinical and/or preclinical data may indicate whether a particular response is likely to be a class effect.
- Exposure to physical and/or mental stresses: The exposure to stress might induce adverse changes in the recipient and provide a logical and better explanation for the event.
- The pharmacology and PK of the study drug: The known pharmacologic properties (absorption, distribution, metabolism, and excretion) of the study drug should be considered.

10.7 Grading of Adverse Event Severity

To report AEs on the eCRFs, the Investigator will use the severity grading as described in NCI-CTCAE, Version 4.03.

Every effort should be made by the Investigator to assess the AE according to CTCAE criteria. If the Investigator is unable to assess severity because the term is not described in NCI-CTCAE Version 4.03, severity of MILD, MODERATE, SEVERE, LIFE-THREATENING, or DEATH may be used to describe the maximum intensity of the adverse event. For purposes of consistency, these intensity grades are defined as follows:

- Mild (Grade 1): does not interfere with patient’s usual function
- Moderate (Grade 2): interferes to some extent with patient’s usual function
- Severe (Grade 3): interferes significantly with patient’s usual function
- Life-threatening (Grade 4): results in immediate risk of patient’s death
- Death (Grade 5): results in patient’s death

Note the distinction between the severity and the seriousness of an AE. A severe event is not necessarily a serious event. For example, a headache may be severe (interferes significantly with patient's usual function) but would not be classified as serious unless it met one of the criteria for serious events.

It is requested that when reporting AEs for which potentially redundant CTCAE terms exist, Investigators utilize the more clinically-oriented terminology (for example, "anemia" is preferable to "hemoglobin decreased").

It is also requested that in the setting of a hypersensitivity reaction or suspected hypersensitivity reaction considered by the Investigator to be related to investigational therapy, that Investigators report both the specific symptoms associated with the reaction (i.e., "urticaria," "chills," "dyspnea," etc.) and also report the appropriate term indicating the hypersensitivity reaction ("allergic reaction," or "infusion related reaction" or "anaphylaxis" if appropriate [General Disorders and Immune System Disorders; CTCAE v4.03, pages 57 and 65]).

11 Statistical Analysis

11.1 General Considerations

Analyses will be performed on all patients that received any quantity of SL-401 (i.e., all treated patients). The baseline value for a given variable is defined as the last measurement for the variable prior to the first infusion of SL-401. Day 1 for each individual patient is defined as the date the patient receives their first infusion of SL-401.

11.2 Determination of Sample Size

The primary objectives of the study are to determine the MTD or the maximum tested dose where multiple DLTs are not observed (Stage 1), and to further characterize the safety profile of SL-401 at this dose (Stages 1 and 2). The anticipated sample size is sufficient to evaluate these objectives.

A secondary objective is to characterize the anti-tumor activity of SL-401. In Stage 2, up to 20 additional patients with MRD as determined locally will enroll and receive SL-401 at either the MTD or maximum tested dose, so that a total of 15 patients with evidence of MRD, as determined centrally, are treated at this dose. The assumptions governing sample size are as follows:

- Null hypothesis: eradication of MRD $\leq 5\%$
- Alternate hypothesis: eradication of MRD $\geq 20\%$
- Type 1 error: 17% one-sided
- Power: $>80\%$

Because no available anti-leukemia therapies (other than allogeneic transplant) are believed to be associated with the eradication of evidence of MRD in this high-risk AML setting, the study

would be considered positive if ≥ 2 of 15 patients in 1st remission (CR) are converted from MRD-positive to MRD-negative status. (In a situation where 1 of 15 patients has eradication of MRD, the results may be considered of interest, given the dearth of efficacious therapy in this setting).

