5.2 Patient Inclusion Criteria

To be included in the study, a patient must meet the following criteria:

1. The patient has a diagnosis of AML according to WHO criteria.
2. The patient received any induction chemotherapy regimen and may have received post-remission consolidation therapy prior to screening.
3. The patient achieved a first or second CR or CRi. For patients without evidence of MRD in CR/CRi, CR (or CRi) must have been initially identified within 12 months prior to screening.

OR

The patient has achieved first or second CR or CRI with evidence of MRD at least 6 months post stem cell transplant without evidence of acute or chronic graft-versus-host disease post-transplant and has not received immunosuppressant therapy for at least 14 days prior to SL-401 therapy.

4. The patient has adverse risk disease or AML for which there is otherwise a substantial risk of relapse, which includes but is not limited to: adverse karyotype, FLT3 internal tandem duplication (ITD) mutation, history of antecedent hematologic disorder (AHD), therapy-related AML, history of requiring more than 1 cycle of intensive induction chemotherapy to achieve first remission, and/or presence of persistent MRD (detected by cytogenetics, molecular markers, or flow cytometry) at any point after the initial induction cycle. (A more comprehensive listing of karyotypes and mutations indicative of high-risk AML is provided as an appendix to the protocol [Section [15.3](#) Appendix C]).
5. For patients enrolling in Stage 2, the bone marrow evaluation determined locally within the previous 6 months indicates the presence of MRD. (A more comprehensive listing of methodologies for evaluation of MRD is provided as an appendix to the protocol [Section [15.4](#) Appendix D]).
6. The patient is not considered to be an immediate candidate for allogeneic stem cell transplant as determined by the investigator.
7. The patient is ≥ 18 years old.
8. The patient has an Eastern Cooperative Oncology Group (ECOG) performance status (PS) of 0-2.
9. The patient has adequate baseline organ function, including cardiac, renal, and hepatic function:
 - Left ventricular ejection fraction (LVEF) \geq institutional lower limit of normal as measured by multigated acquisition scan (MUGA) scan or 2-dimensional (2-D) echocardiogram (ECHO) within 28 days prior to start of therapy and no clinically significant abnormalities on a 12-lead electrocardiogram (ECG)
 - Serum creatinine ≤ 1.5 mg/dL

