3.8. Subgroup Analyses

Subgroup analyses will be performed for efficacy analyses by MRD status and line of therapy in study (First-Line or Relapsed/Refractory).

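### The ≥ 2 of 15 MRD success rule pools post-transplant patients under a 5% null whose rationale sets allogeneic transplant aside, and no planned analysis shows whether a positive result depends on them

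*Protocol*

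**What the plan says.** The study has no control arm, so the null rate is the comparator. Protocol 11.2 sets a null of at most 5% and an alternative of at least 20%, with "Type 1 error: 17% one-sided" and power above 80%. Stage 2 is sized "so that a total of 15 patients with evidence of MRD" by central assessment. The rule is 2 or more conversions among 15 patients in first remission. Its rationale begins "Because no available anti-leukemia therapies (other than allogeneic transplant) are believed to be associated with the eradication of evidence of MRD", and SAP 3.1 repeats it. SAP 3.2 makes MRD eradication in Stage 2 the only endpoint with a formal hypothesis test.

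The second limb of criterion 3 (Protocol 5.2) opens a post-transplant route: "The patient has achieved first or second CR or CRI with evidence of MRD at least 6 months post stem cell transplant". The patient must be free of graft-versus-host disease and one who "has not received immunosuppressant therapy for at least 14 days prior to SL-401 therapy". Criterion 6 keeps out immediate candidates for allogeneic transplant, not patients already transplanted.

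The endpoint (Protocol 11.5.1, SAP 4.3.1) covers every patient with MRD before SL-401. The mITT population (SAP 2.1) has no transplant condition. On subgroups, SAP 3.8 says: "Subgroup analyses will be performed for efficacy analyses by MRD status and line of therapy in study (First-Line or Relapsed/Refractory"). Protocol 11.5 names disease and line of therapy. None of these identifies prior transplant.

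**The concern.** The rationale names one treatment that can eradicate MRD, and the eligibility criteria admit patients who have already had a transplant. Criterion 5 requires MRD for Stage 2 and the post-transplant route also requires it, so these patients meet the MRD condition for the stage that is tested. They are judged against the same 5%, although the text offers no rate for them.

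The threshold is two conversions. If one or both came from transplanted patients, a reader of the planned tables could not tell, and could not separate a drug effect from whatever background rate applies after transplant. The result of the study's only formal test would then not answer the question for which its null was set.

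**Working it through.** **Inputs.** From Protocol 11.2: n = 15, threshold 2, null 5%, alternative 20%. Not in the documents, so assumed: k, the number of post-transplant patients among the 15, and r, their conversion rate without an SL-401 effect.

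**Step 1: the plan's own figures.**
- Type I error = 1 − 0.95^15 − 15 × 0.05 × 0.95^14 = 1 − 0.4633 − 0.3658 = 17.1%.
- Power = 1 − 0.80^15 − 15 × 0.20 × 0.80^14 = 1 − 0.0352 − 0.1319 = 83.3%.

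Both agree with the stated 17% and above 80%.

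**Step 2: a mixed population.** With 15 − k patients at 5% and k at r:
- P(0) = 0.95^(15−k) × (1 − r)^k
- P(1) = P(0) × [(15 − k) × 0.05/0.95 + k × r/(1 − r)]
- P(2 or more) = 1 − P(0) − P(1)

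Example with k = 3 and r = 10%: P(0) = 0.95^12 × 0.90^3 = 0.5404 × 0.729 = 0.3939; P(1) = 0.3939 × (0.6316 + 0.3333) = 0.3801; P(2 or more) = 22.6%.

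| Assumed r | k = 1 | k = 3 | k = 5 |
|---|---|---|---|
| 2% | 16.0% | 13.9% | 11.9% |
| 5% | 17.1% | 17.1% | 17.1% |
| 10% | 18.9% | 22.6% | 26.4% |
| 15% | 20.7% | 28.3% | 36.0% |
| 20% | 22.5% | 34.1% | 45.5% |

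The direction depends entirely on whether r is below or above 5%. The 20% row uses the plan's alternative rate as an upper illustration. Nothing in the documents supports it as a background rate.

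**Step 3: the rule without transplanted patients.** If they are removed and not replaced, a threshold of 2 gives:

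| n | Type I error at 5% | Power at 20% |
|---|---|---|
| 15 | 17.1% | 83.3% |
| 14 | 15.3% | 80.2% |
| 13 | 13.5% | 76.6% |
| 12 | 11.8% | 72.5% |

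**Step 4: enrolment as recorded.** SAP 3.1 reports 9 Stage 2 patients at database lock. If all 9 entered the test with the threshold kept at 2, the error would be 7.1% and the power 56.4%. With 3 of the 9 post-transplant, the error would be 16.7% at an assumed r of 15% and 22.3% at 20%.

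**The case against.** A reader might infer that the 17% error is wrong or inflated. The documents do not support that. Patients on the post-transplant route are MRD-positive at least 6 months after transplant, so in them the transplant did not clear MRD or did not keep it cleared. Naming transplant as a treatment that can eradicate MRD does not say that patients still positive months later convert without further treatment. A continuing graft effect, or an effect of stopping immunosuppression shortly before SL-401, would have to be assumed. This objection stands: the inflation is conditional, and below 5% the error falls.

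Four further limits also stand.
- No source or derivation is given for the 5%. The sentence about available therapies directly supports the success rule, and its link to the null rate is a reading.
- Criterion 3 says stem cell transplant without a type. The graft-versus-host and immunosuppressant conditions point to allogeneic transplant, but autologous is not excluded.
- The rule is worded for first remission. Taken literally, that leaves out second-remission post-transplant patients. First-remission ones still count, so the issue narrows but remains.
- MRD eradication is a secondary endpoint in a dose-finding study. Prior AML treatment is collected (Protocol 8.2) and by-patient listings are planned (SAP 4.2 and 4.3), so converters' histories could be looked up afterwards.

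The last point does not settle the matter. A look at listings after the result is known does not fix beforehand how a conversion in a transplanted patient will be read.

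A reader might also conclude that these patients should be dropped from the success rule. That is not compelled: without replacement, power falls below the stated 80% at n = 13, in exchange for removing a bias whose size and direction are unknown.

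**Conclusion.** The point holds as a problem of interpretation. One 5% null is applied to a group that includes patients outside its stated rationale, and no planned analysis separates them. Because two conversions decide the result, a positive finding could depend on transplanted patients and could not then be taken as SL-401 activity in the intended setting.

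The 17% itself stands as computed, and the documents do not show that it is exceeded. With 3 of 15 patients post-transplant, the error would run from 13.9% to 34.1% as their background rate runs from 2% to 20%. The count and the rate are both assumptions. The point also assumes that at least one first-remission post-transplant patient is counted and that the transplants are mainly allogeneic.

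**What to change.** - **SAP 3.8:** add prior stem cell transplant (yes or no, with allogeneic or autologous type) to the efficacy subgroups.
- **SAP 4.3.1:** present the MRD conversion rate with an exact confidence interval by prior transplant. Give the result of the success rule twice: for all centrally MRD-positive patients, and for those without prior allogeneic transplant. State type I error and power at the actual n each time (for example 13.5% and 76.6% at n = 13).
- **Protocol 11.2 and SAP 3.1:** state that a positive result that depends on post-transplant conversions will not be read as SL-401 activity against the 5% null.

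Eligibility and the main denominator do not change. Prior AML treatment is already collected, so the cost is wording and one extra table; transplant type should be confirmed as recorded. The drawback is that the subgroups will be small and their intervals wide.
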